- Describe the study, providing details regarding the study intervention (drug, device, physical procedures, manipulation of the subject or the subject's environment, etc.). Discuss justifications for placebo control, discontinuation or delay of standard therapies, and washout periods if applicable. Identify procedures, tests and interventions performed exclusively for research purposes or more frequently than standard of care. Include alternative therapies, concurrent therapies discontinued per protocol, risk benefit ratio, and use of tissue/specimens. Discuss monitoring during washout periods if applicable. Include brief description of follow-up, if any.

Research Plan. Women with breast cancer (N=190) will be randomly assigned with equal allocation to: 1) mPCST-Community or 2) mHealth-Education. Both conditions (mHealth-Ed) will involve four 50-minute individual sessions conducted over the course of 8 weeks with videoconferencing at the participant's community-based clinic or at the participant's home. Participants in mPCST-Community and mHealth-Ed will receive a smartphone to extend the intervention into their home environment. The study mobile application will provide participants in the mPCST-Community with: a mobile application that provides text and audio of intervention content tailored for low literacy, modeling video-clips, stories from other patients with pain, and other mPCST-Community materials (e.g., relaxation audio). The mPCST-Community participants will also enter daily pain, fatigue, and hassles levels and daily coping skills practice; this data will be used to send personalized messaging encouraging skills use. Innovative components of the mPCST-Community intervention include: new hybrid delivery modality (i.e., videoconferencing in community clinic, smartphone) to make such a protocol accessible to patients in medically underserved communities, adaptation for low-literacy patients, and use of personalized messaging. The therapist delivering the intervention will be at Duke University Medical Center and the participants will be at their community-based clinic. Participants may also choose to complete sessions in their home environment. mHealth-Ed participants will be given smartphones to access education session information, receive cancer education based messaging, and an education app. Participants will complete assessments at baseline, post-intervention, and at a 3- and 6-month post-intervention follow-up.

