Participants. Participants will be women with a diagnosis of breast cancer within the last three years. Stages I-IV will be included as recently published work suggests increased life expectancy for patients with advanced cancer⁸⁷ and significant pain is possible from both the tumor and cancer treatments during this time period.¹⁹⁻²³ Other eligibility criteria are: 1) being ≥ 18 years old, 2) having a life expectancy of ≥ 12 months, 3) report experiencing pain on at least 10 days in the last month and rate their pain in the past week as a 4 or greater on a 0-10 scale. The combination of these items assess patients level of persistent pain (in the last month) and pain severity with an accurate recall period (i.e., last week; ≥ 4). Exclusion criteria include: 1) cognitive impairment as indicated by a baseline Folstein Mini-Mental Status Examination of <25 ⁸⁸ and the Rapid Estimate of Adult Literacy in Medicine, Revised (REALM-R) or through medical chart review indicated by a baseline Folstein Mini-Mental Status of Examination <25 2) brain metastases, 3) presence of a severe psychiatric condition or a psychiatric condition (e.g., suicidal intent) that would contraindicate safe participation in the study as indicated by the medical chart, treating oncologist, or medical/study staff interactions, or 4) current or past (<6 months) engagement in PCST for cancer.

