Statistical Power & Analyses. The approach to the analysis will utilize repeated measures mixed model analysis of covariance. For simplicity of exposition, this is described with the outcome not as a vector of 4 measurements, but instead as the analysis of a series of one-dimensional difference scores, with each difference score taken relative to the baseline measurement. Model covariates will include baseline score, variables unexpectedly unbalanced between groups at baseline (i.e., to account for potential bias), and variables that may be correlated with the outcome (i.e., to increase precision). Potential covariates include depression, social support, physical activity, medical/demographic variables including cancer treatments, and recruitment site.

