Aim 1: Test the extent to which mPCST-Community reduces pain severity (primary outcome), pain interference, fatigue, physical disability, and psychological disability. Demographic, medical characteristics and other potential covariates will be summarized. Focusing on pain severity as an illustration of our analytical methods, we will first describe the pattern of missing data over time by group – paying particular attention to the possibility of differential drop-out. We will then analyze three outcome variables: post-intervention minus baseline addresses the mechanistic hypothesis pertaining to immediate effects of the intervention; 3 months minus baseline addresses the (primary) hypothesis of short-to-medium term effects of the intervention; and 6 months minus baseline addresses the hypothesis of longer-term effects of the intervention. Each hypothesis will be tested using the main effect of study group, adjusting for covariates. We anticipate relatively little missing data for the primary and mechanistic hypotheses – the issue of missing data will be addressed through sensitivity analyses using propensity scoring (which would essentially allow us to “compare likes with likes” even in the presence of differential drop-out).¹³⁰ **Statistical power.** For purposes of estimating power, we define pain severity as the primary outcome variable. Using the methods of Cohen, and assuming an effective sample size of 72 per group (i.e., 90 per group minus 20% attrition), an unadjusted analysis has 80% power to detect an effect size of approximately 0.48. This is a moderate effect size which is a reasonable estimate of the minimum clinically important difference in patients with pain and practically important and consistent with what will need to be shown for adoption of the intervention in clinical practice.¹³¹⁻¹³³ Further support for this effect size is gained from our pilot work that has been consistent (within the constraints

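### Does the primary pain analysis use baseline pain twice, as an outcome and as a covariate, and so spoil the 3-month test?

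*Combined protocol and SAP*

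**What the plan says.** The opening paragraph of Statistical Power & Analyses (under Data Analysis & Statistical Considerations) names the method: "The approach to the analysis will utilize repeated measures mixed model analysis of covariance". It continues: "For simplicity of exposition, this is described with the outcome not as a vector of 4 measurements", but as a series of single change scores, "with each difference score taken relative to the baseline measurement". The next sentence begins the covariate list: "Model covariates will include baseline score".

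The Research Plan under Design & Procedures gives the visits: "Participants will complete assessments at baseline, post-intervention, and at a 3- and 6-month post-intervention follow-up".

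Aim 1 then sets out what is analysed. There are three outcome variables, one per follow-up visit, each minus baseline. Of these, "3 months minus baseline addresses the (primary) hypothesis of short-to-medium term effects of the intervention". Each hypothesis is tested by the group main effect with covariate adjustment. On power, with 72 per group after attrition, "an unadjusted analysis has 80% power to detect an effect size of approximately 0.48".

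The plan does not give the mixed model's covariance structure, its visit terms, or the form of the 3-month contrast within it.

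**The concern.** The change scores are introduced as a device for explanation, which suggests that the real model has four measurements as its outcome. There are exactly four assessments, so one of the four must be baseline. If the covariate list belongs to that model, baseline pain is regressed on itself.

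This would affect the primary test. Depending on the covariance structure and the contrast, the model would fail to fit, understate the standard error at 3 months, or lose the precision from baseline adjustment. That precision is part of why the plan calls its power calculation conservative. None of these effects needs dropout or an unusual pattern of treatment effects.

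**Working it through.** **Inputs.** From the plan: 72 per group, effect size 0.48, SD 2.0 (the example in the power section), hence a difference of 0.48 × 2.0 = 0.96 points. Assumed, because the plan is silent: two-sided 5% level, visit correlation r from 0.3 to 0.7, equal SDs, complete data.

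**1. The plan's own figure.** The unadjusted standard error is 2.0 × √(2/72) = 0.333. The noncentrality is 0.96/0.333 = 2.88, and power from the noncentral t with 142 df is 81.6%. The stated 80% is reproduced, slightly on the cautious side.

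**2. The test that Aim 1 describes.** Write Y0 and Y3 for pain at baseline and 3 months, and G for group. The model is

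Y3 − Y0 = a + θG + cY0 + error.

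Moving Y0 to the right gives Y3 = a + θG + (1 + c)Y0 + error. The group effect θ, its standard error and its test are the same as in analysis of covariance of the 3-month score. Baseline is not an outcome row. The residual variance is 4(1 − r²), so the standard error is √(2 × 4(1 − r²)/72).

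| r | SE | Power for 0.96 points |
|---|---|---|
| 0.3 | 0.318 | 85% |
| 0.5 | 0.289 | 91% |
| 0.7 | 0.238 | 98% |

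Simulation under no effect (8,000 trials per setting, 72 per group) gave false-positive rates of 5.0 to 5.2%. The test is valid, and every power figure exceeds the unadjusted 81.6%, so calling the calculation conservative holds.

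**3. The double-use model, for comparison.** Suppose all four scores are outcomes and baseline is also a covariate with slope b.

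- *Unstructured covariance.* The baseline residual is proportional to (1 − b), so the profile log-likelihood is constant − n log|1 − b|, which is unbounded as b approaches 1. In one simulated trial with n = 144 it went from −790.4 at b = 0.9 to −458.8 at b = 0.99. The rise of 331.6 equals 144 × log 10. There is no proper fit.
- *Compound symmetry, group difference read at 3 months.* False-positive rate 7.5 to 8.4% for r from 0.3 to 0.7 (8,000 trials per setting).
- *Compound symmetry, 3 months minus baseline.* The covariate cancels, leaving a raw change score. False-positive rate 4.7 to 4.9%. The variance is 8(1 − r), giving power of 68%, 82% and 96% at r = 0.3, 0.5 and 0.7. This is valid but less efficient than step 2.
- *Group effect averaged over all four visits.* False-positive rate 5.3 to 5.6%, but with 0.96 at every follow-up visit it estimates about 0.72, since (0 + 0.96 + 0.96 + 0.96)/4 = 0.72.

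Entry requires that patients "rate their pain in the past week as a 4 or greater on a 0-10 scale". Shorter runs with baseline truncated at 4 (700 trials per setting) showed the same pattern.

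**4. Which model the text supports.** The four-measurement vector appears only in a clause saying how the outcome is not described. The covariate list follows directly on the change-score description. Aim 1 then commits to three change-score outcomes and a covariate-adjusted group comparison for each. The double-use model needs the covariate list to be carried over to a model that the plan mentions but does not specify.

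**The case for a change.** The strongest argument for a change is that the plan names a mixed model and treats the change scores as a simplified account of it. Two readings of the primary test then exist, they are not equivalent, and one is faulty. Nothing on covariance or contrasts settles the matter, and one or two sentences would remove the doubt at no cost.

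The ambiguity is real, and the calculations for the faulty model are correct. Three things limit what follows from them:

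- The 8% error rate needs a shared variance across visits, model-based standard errors, and a group difference read at the 3-month visit. The plan specifies none of these for the mixed model. The contrast it does name, 3 months minus baseline, keeps its error rate near 5% even in the double-use model under compound symmetry.
- The unbounded likelihood would not produce a silent wrong answer. The slope runs to 1 and the baseline variance to zero, which an analyst would see at once.
- The power loss of the raw change score takes it below 80% only at assumed correlations under about 0.5, and only on the double-use reading.

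What stands is that a sentence naming the outcome rows would be tidier.

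**Conclusion.** The concern does not call for a change. Followed as Aim 1 sets it out, the primary test is a baseline-adjusted comparison of 3-month change. Its simulated false-positive rate is 5.0 to 5.2%, and its power for 0.96 points with 72 per group is about 85 to 98%. The stated 80% for the unadjusted comparison is reproduced at 81.6% and does not depend on the mixed model.

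The gap is one of detail: outcome rows, covariance structure and contrast are not written out. A competent analyst would take the three post-baseline scores, or the three change scores, as outcome with baseline as covariate only. The other sound option is four scores with the arms held equal at baseline and no baseline covariate. Either gives a valid 3-month test.

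These figures assume a two-sided 5% level, SD 2.0 at each visit, complete data and visit correlations of 0.3 to 0.7. The equivalence in step 2 needs none of these assumptions.

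### Does leaving the primary model's covariates unlisted, apart from the baseline score, undermine the primary test?

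*Combined protocol and SAP*

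**What the plan says.** Under Data Analysis & Statistical Considerations, the paragraph Statistical Power & Analyses names one certain covariate: "Model covariates will include baseline score". Two further classes may join it: "variables unexpectedly unbalanced between groups at baseline (i.e., to account for potential bias), and variables that may be correlated with the outcome". The text gives each class a purpose, protection against bias for the first and precision for the second. It then names candidates: "Potential covariates include depression, social support, physical activity, medical/demographic variables including cancer treatments, and recruitment site".

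The Aim 1 paragraph sets the primary comparison: "3 months minus baseline addresses the (primary) hypothesis of short-to-medium term effects of the intervention". The test is stated in one sentence: "Each hypothesis will be tested using the main effect of study group, adjusting for covariates". The covariates are not listed again there.

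No section defines imbalance, sets a screening threshold, caps the number of covariates or says when the list is settled. The documents do not describe blinding of the analyst. The Aim 3 paragraph does name its covariates (baseline resource use and EQ-5D weights).

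**The concern.** Several different models fit this text: baseline score only, baseline plus whatever proves imbalanced, or baseline plus every candidate. If the model were chosen after the treatment effect had been seen under each, the false-positive rate of the primary test would exceed its nominal level, and a reader could not tell.

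The imbalance trigger also looks unsound. The Research Plan says that women "will be randomly assigned with equal allocation", so any baseline imbalance is chance. Imbalance in a variable unrelated to pain does no harm, and a variable related to pain is worth adjusting for whether or not it is imbalanced. The plan also calls its power calculation conservative because of covariates that it has not finally named.

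**Working it through.** **1. The plan's own power figure.** Inputs from the Aim 1 paragraph: 90 per group less 20% attrition, so 90 × 0.80 = 72 per group, and an effect size of 0.48, unadjusted. Two-sided alpha of 0.05 is assumed, since none is stated.

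- Standardised shift: 0.48 × √(72/2) = 0.48 × 6 = 2.88.
- Normal approximation: Φ(2.88 − 1.96) = Φ(0.92) = 82.1%. The t-test gives 81.6%.
- Effect detectable with 80% power (t-test): 0.470.

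The stated 80% at about 0.48 is reproduced.

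**2. Does the claim of conservatism need the unnamed covariates?** Adjustment turns the effect 0.48 into 0.48/√(1 − R²). For assumed R² of 0.10, 0.25 and 0.40, power is 85.4%, 91.0% and 95.8%. The baseline score alone, at an assumed correlation of 0.5, gives R² = 0.5² = 0.25. The one covariate that is fixed therefore already supports the claim under that assumption.

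**3. Error rate of the rule as written.** The documents give no covariate strengths, so these are assumed: ANCOVA on the 3-month outcome, 72 per arm, baseline r = 0.5, and six independent candidates with r = 0.10, 0.15, 0.20 or 0.25 each. The six add 6 × r² = 6%, 13.5%, 24% or 37.5% of outcome variance. A candidate enters if it is imbalanced at p<0.05 or correlated with the outcome at p<0.05. Both thresholds are assumed.

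- Two-sided error: 4.8–5.0% in 24,000 null trials per scenario (Monte Carlo standard error about 0.14 points).
- Smaller separate runs of 3,000–4,000 trials: 4.1–5.2% for imbalance screening alone, and 4.7–5.3% for outcome-correlation screening at p<0.10. The departures from 5% are small, and the largest is downward.

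**4. Would a short fixed list do better?** Power at a true effect of 0.40 SD:

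| r of each candidate | Plan's rule | Three of the six, fixed |
|---|---|---|
| 0.10 | 77.4% | 77.3% |
| 0.15 | 80.4% | 80.3% |
| 0.20 | 86.5% | 84.2% |
| 0.25 | 94.8% | 88.6% |

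The fixed short list gains nothing. Always including all six would gain 0–3 points over the rule. If the candidates proved useless, however, six plus seven site indicators would cost power: 74.2% against 78.9% with baseline only.

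**5. What deliberate selection would do.** The three sets are baseline only, the plan's rule, and all six.

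| r of each | Error, best of three sets | Error, best of all 64 subsets | Sets disagree on p<0.05, effect 0.40 | Same, effect 0.48 |
|---|---|---|---|---|
| 0.10 | 6.8% | 8.9% | 9% | 5.0% |
| 0.15 | 7.7% | 11.2% | 13% | 6.8% |
| 0.20 | 8.6% | 14.2% | 17% | 8.0% |
| 0.25 | 8.6% | 19.2% | 20% | 8.8% |

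The two error columns require the analyst to fit the alternatives, look at the treatment p-value in each, and report the smallest. The disagreement columns show only that different valid models of the same data sometimes fall on different sides of 0.05. The plan is powered at 0.48, so the last column is the relevant one.

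**6. Difference scores and baseline.** The section says that "this is described with the outcome not as a vector of 4 measurements" and presents differences from baseline as a simplification. If y₃ − y₀ = a + τ·group + β·y₀, then y₃ = a + τ·group + (β + 1)·y₀. The group effect τ is the same, so adjusting a change score for its baseline is ordinary ANCOVA and creates no second problem.

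**The case for a change.** The best case for a change is that the wording could be tightened almost without cost. Naming a closed list before outcomes are linked to group would need no extra patients. If three added covariates proved useless, the loss would be about 1 point of power (78.9% to 77.7% at 0.40 SD). The plan shows with Aim 3 that it can be this specific, and no later analysis document is mentioned. On principle, a covariate should earn its place by expected prognostic value and not by chance imbalance. With free choice among subsets, the possible error under these assumptions reaches 19.2%.

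Some of this stands. The list is open, and a named list would let a reader confirm that the model was not picked for its result. The argument about chance imbalance is correct as a matter of principle. But following the imbalance trigger does not inflate error, and replacing the rule with a short fixed list adds no power. The larger error figures measure a practice that the plan neither describes nor invites. The natural reading of the second class is variables expected to be prognostic, and the section supplies the candidates and the purpose. Choosing a few of them, and deciding whether to include site, is a judgement that any analyst drawing on these candidates must make.

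**Conclusion.** The observation is accurate, but it identifies missing detail and not a faulty test. The outcome, the time point, the group comparison and the most obvious covariate are all fixed. Applied as written, with assumed screening thresholds, the covariate rule holds two-sided error near 5% and gives up at most about 3 points of power against always including six candidates. The 7–9% error rate, and the higher values under free subset choice, require selection on the result. At the plan's effect of 0.48, the choice among three reasonable covariate sets changes the significance verdict in about 5–9% of trials.

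These sizes rest on assumed values: baseline correlation 0.5, six independent candidates of equal strength, and 72 analysed per arm. Unequal strengths would alter the comparison in step 4, because a fixed list of the strongest candidates would do better than shown. The near-5% error of the mechanical rule held in every scenario tried. No change to the plan follows.

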Aim 3: To evaluate cost, cost-effectiveness and practicality of mPCST-Community. **Analyses.** We will use patient-level data to test for differences between mPCST-Community and the Health-Edu conditions on medical resource use, medical costs and productivity costs. We will use generalized linear models specified using negative binomial error distributions and log links for resource use and gamma error distributions and log links for costs. We will apply mixed-effects linear regression models to test for interactions between study interventions and time on EQ-5D-derived preference weights across the 6-month follow-up period. Baseline resource use and EQ-5D weights will be included as covariates in regression models. For each patient will compute quality-adjusted life-years (QALY) using the trapezoidal rule applied to EQ-5D weights at baseline, post-intervention, 3 months and 6 months. Because the mHealth-Ed control was designed to control for patient contact time and does not represent standard care, accounting for the costs of providing this condition and patient time spent participating would inappropriately offset the costs associated with the mPCST-Community intervention. Therefore, we will modify our calculation of the numerator of incremental cost-effectiveness ratio (ICER) in which we will calculate the difference in mean medical costs and productivity costs between the mPCST-Community and mHealth-Ed control groups then add direct costs of resources required to provide mPCST-Community as well as participant time costs. To compute the difference in QALYs, we will subtract mean QALYs in the mHealth-Ed condition from mean QALYs in the mPCST-Community condition. Then, we will divide the estimated difference in mean costs by the difference in mean QALYs and generate a 95% confidence interval constructed using nonparametric bootstrapping. We then will calculate net health benefits (QALY* λ – Cost, where λ represents maximum willingness to pay per QALY) for each patient, and apply linear regression analysis to evaluate whether intervention and patient baseline characteristics are associated with improved cost-effectiveness. In sensitivity analyses, we will evaluate the impact of: (1) applying various durations of sustained benefit beyond the 6-month follow-up period; (2) excluding productivity gains/costs; and (3) assuming patients could participate in videoconferencing at home. To evaluate practicality and sustainability of PCST-Community, we will assess accrual, participant retention, and intervention protocol adherence.

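### The only test named for the EQ-5D weights is group-by-time with baseline as a covariate; read directly, it has power equal to alpha against a benefit that is constant over follow-up

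*Combined protocol and SAP*

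**What the plan says.** All references are to the combined protocol and SAP.

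- *Data Analysis & Statistical Considerations*, Aim 3 Analyses: mixed-effects linear models will be used to "test for interactions between study interventions and time on EQ-5D-derived preference weights across the 6-month follow-up period". The next sentence adds: "Baseline resource use and EQ-5D weights will be included as covariates in regression models". The section does not list the time levels of the EQ-5D model or say whether baseline is also a row of the outcome. It names no group main effect, averaged contrast or visit contrast for the weights.
- *Design & Procedures*, Research Plan: "Participants will complete assessments at baseline, post-intervention, and at a 3- and 6-month post-intervention follow-up". That is one baseline and three post-baseline visits.
- *Statistical Power & Analyses*, opening paragraph, on the general approach: "this is described with the outcome not as a vector of 4 measurements" but through change scores, and "Model covariates will include baseline score". This leaves open a model in which baseline has both roles.
- Aim 1, for contrast: "Each hypothesis will be tested using the main effect of study group, adjusting for covariates".
- Aim 3 also computes QALYs "using the trapezoidal rule applied to EQ-5D weights at baseline, post-intervention, 3 months and 6 months", and for the ICER "we will subtract mean QALYs in the mHealth-Ed condition from mean QALYs in the mPCST-Community condition".

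**The concern.** A group-by-time interaction asks whether the difference between arms changes over the time levels in the model. Once baseline has moved to the covariate side, those levels are the three follow-up visits. A benefit reached by the end of the sessions and held to 6 months then lies wholly in the group term, and the plan does not name a test of that term. The named test would favour an effect that wears off over one that lasts.

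Aim 1 tests the group effect, and the plan gives no reason for Aim 3 to differ. At stake is the only stand-alone test of utilities in the plan. A lasting improvement in EQ-5D could be read from it as no evidence of benefit.

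**Working it through.** **Inputs from the plan.** 72 per arm after attrition (90 × 0.8 = 72) and three post-baseline visits. The plan gives no EQ-5D power, SD, correlation or effect size.

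**Plan's own figure.** It concerns pain severity: 80% power at an effect size of about 0.48. With 72 per arm and two-sided alpha 0.05 (assumed; not stated), the noncentral t gives 81.6%, so the figure reproduces to within 2 points.

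**Assumptions for EQ-5D.** SD σ = 0.20, exchangeable correlation ρ = 0.4, 0.6 or 0.7, complete data, two-sided alpha 0.05, constant benefit δ = 0.06 (0.06/0.20 = 0.30 SD).

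**Interaction test.** With balanced data and a random intercept, group-by-time is a within-participant contrast. A baseline covariate is constant within a participant and leaves it essentially unchanged. With T outcome rows and arm difference δ_t at row t, the noncentrality is

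λ = (n/2) × Σ(δ_t − mean δ)² / [σ²(1 − ρ)], on T − 1 and (2n − 2)(T − 1) degrees of freedom.

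*Three follow-up rows, constant benefit.* Every δ_t equals the mean, so the sum is 0, λ = 0 and power equals alpha. This holds for any δ, σ and ρ. Simulation at a constant 0.48 SD (10,000 trials per setting, ρ = 0.3 to 0.7) gave 4.8% to 5.3%, against 99.0% to 99.9% for the baseline-adjusted group effect.

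*Three follow-up rows, fading benefit 0.10, 0.06, 0.02.* The mean is again 0.06. The sum is 0.04² + 0 + 0.04² = 0.0032, and λ = 36 × 0.0032 / [0.04(1 − ρ)] = 4.8, 7.2, 9.6. On 2 and 284 df, power is 48%, 66%, 79% for ρ = 0.4, 0.6, 0.7.

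*Four rows, baseline included, differences 0, 0.06, 0.06, 0.06.* The mean is 0.045. The sum is 0.045² + 3 × 0.015² = 0.0027, and λ = 36 × 0.0027 / [0.04(1 − ρ)] = 4.05, 6.08, 8.10 on 3 and 426 df.

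**Baseline-adjusted group contrast averaged over the three follow-ups.** Residual variance is σ²[(1 + 2ρ)/3 − ρ²], SE = √(2 × variance / 72), with 141 df. For ρ = 0.6: 0.04 × (0.7333 − 0.36) = 0.01493; SE = 0.0204; 0.06/0.0204 = 2.95.

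| Constant 0.06 | ρ = 0.4 | ρ = 0.6 | ρ = 0.7 |
|---|---|---|---|
| Interaction, 3 follow-up rows | 5% | 5% | 5% |
| Interaction, 4 rows | 36.0% | 52.0% | 65.6% |
| Adjusted group contrast | 76.9% | 83.3% | 89.5% |

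Simulations under the same assumptions agree to within about 2 points: 36% to 65% for the four-row interaction and 77% to 90% for the group contrast. At a constant 0.08 the formula gives 60%, 79%, 90% for the four-row interaction and 95%, 97%, 99% for the group contrast.

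**The case against.** **The plan may intend four rows.** The general description mentions four measurements, and the covariate sentence refers to regression models at large. This stands: the documents do not settle the rows. On that reading the interaction does detect a constant benefit, with 70%, 85% and 98% power at 0.48 SD for ρ = 0.3, 0.5 and 0.7.

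**A reader might infer that baseline as both row and covariate makes the test invalid.** The documents and the check do not support that. Under no effect, the exact within-participant test rejected 5.0% to 5.1% (10,000 trials per setting), and a mixed model with baseline in both roles rejected 5.0% (300 fits). The double use is untidy but does not inflate error here.

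**A reader might also infer that Aim 3 could not show a stable benefit at all.** That goes too far. A model with group-by-time would ordinarily contain the group term too. The Aim 3 hypothesis concerns cost per QALY, and the mean QALY difference, the bootstrapped ICER interval and the net-benefit regression all carry a stable benefit. With visits placed at months 0, 2, 5 and 8 and a constant 0.48 SD, a test of mean QALYs would have 80% to 94% power unadjusted and about 99% or more adjusted for baseline. But the plan states no separate test of QALYs, and the ICER and net benefit mix utility with cost. Nor does the plan say how a non-significant interaction would be reported.

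**The numbers are assumed.** This is true of every figure that depends on σ, ρ or δ. The result that power equals alpha does not depend on them.

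**Conclusion.** The point holds for the named EQ-5D test. On the most direct reading, that test has power equal to alpha (about 5%) against a benefit constant over follow-up, and it favours a fading effect. On the other reading it is valid but inefficient for a constant benefit: about 36% to 65% power against 77% to 90% for the adjusted group contrast, given 72 per arm and assumed SD 0.20, correlation 0.4 to 0.7, benefit 0.06 and complete data. At ρ = 0.6, the same wording therefore permits analyses with about 5% or about 52% power. That choice should be made before the data are seen.

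The reach is limited to the stand-alone utility test under a secondary aim. The change is worth making because the plan has no other test of utilities alone.

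**What to change.** In the Aim 3 analyses:

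1. State the EQ-5D outcome rows as post-intervention, 3 and 6 months, with baseline EQ-5D as a covariate and terms for visit, group and group-by-visit.
2. Name the baseline-adjusted group contrast, averaged over the three visits, as the test of benefit.
3. Report the visit-specific contrasts with confidence intervals.
4. Keep group-by-visit as a supplementary description of whether the effect changes over follow-up.

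The cost is a few sentences of SAP text. The data, visits and class of model stay the same.
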